4. History of any venous thromboembolism, TIA, intracranial hemorrhage, neoplasm, arteriovenous malformation, vasculitis, bleeding disorder, coagulation disorders or screening blood tests that indicate altered coagulability (e.g. platelet count, aPTT, PTT or TT tests).
5. Patients with INR $>$ ULN at visit 1.
6. Patients with total bilirubin $>$ ULN at visit 1 that is not due to Gilbert's syndrome.
7. Patients with $>30\%$ increase in ALT, total bilirubin, or INR between visit 1 to visit 2, unless both results (visit 1 and visit 2) are within the reference range.
8. Patients with serum creatinine $>$ ULN according to the gender at Visit 1.
9. Patients with abnormal total creatine kinase (CK) OR lipase OR amylase at Visit 1.
10. Unstable cardiovascular disease, including:
 - unstable angina, (i.e., new or worsening symptoms of coronary heart disease within the past 3 months), acute coronary syndrome within the past 6 months, acute

myocardial infarction in the past 3 months or heart failure of New York Heart Association class (III – IV) or worsening congestive heart failure, or coronary artery intervention, within the past 6 months

- history of (within prior 3 months) or current unstable cardiac dysrhythmias
- uncontrolled hypertension (systolic blood pressure [BP]>160 mmHg and/or diastolic BP >100 mmHg)
- stroke or transient ischemic attack within the prior 6 months

11. History of malignancy in the past 5 years and/or active neoplasm with the exception of resolved superficial nonmelanoma skin cancer.
12. Contraindications to Saroglitzaz magnesium or has any conditions affecting the ability to evaluate the effects of Saroglitzaz magnesium.
13. Known allergy, sensitivity or intolerance to the study drug, comparator or formulation ingredients.
14. Participation in any other clinical study within the previous 3 months of screening.,
15. Illicit substance abuse within the past 6 months.
16. History or other evidence of severe illness or any other conditions that would make the patient, in the opinion of the investigator, unsuitable for the study (such as poorly controlled psychiatric disease, HIV, coronary artery disease or active gastrointestinal conditions that might interfere with drug absorption).

Methodology:

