This is a Phase 2 prospective, multicenter, randomized, double-blind, placebo-controlled study planned to enroll a total of 36 patients from ~10-12 sites with a diagnosis of PBC who meet the study's inclusion/exclusion criteria. The study will be conducted over a period of up to 26 weeks and will include a 6-week Screening Phase, a 16-week double-blind Treatment Phase and a safety follow-up visit after 4 weeks. Six patients in each group are planned for pharmacokinetic assessment therefore a total of 18 patients will be included. Additional patients may be enrolled into the study to ensure the pharmacokinetic assessment is performed on at least 6 completed patients in each treatment arm.

Screening Phase

- Visit 1 (Day -42): Patient eligibility for participation in the study will be assessed. Medical history will be obtained and physical examination, electrocardiogram (ECG) and laboratory evaluations (including serology, [anti-nuclear antibody, smooth muscle antibody and serum immunoglobulin level G], clinical chemistry, hematology, liver biochemistries, and urinalysis) will be performed. In patients with ANA or SMA antibody positive titers, a liver biopsy must have been performed to rule out autoimmune hepatitis or overlap syndrome. Female patients will undergo a pregnancy test. Serum ALP must be ≥ 1.67 upper limit of normal (ULN) to

proceed further in the study.

- Visit 2 (Day -14 to -7): Liver biochemistries (ALT, ALP, total bilirubin (TB) and INR will be re-measured approximately 4 weeks from Day -42 to determine eligibility.

Elevated ALP must be ≥ 1.67 ULN on 2 occasions in the Screening Phase and is necessary for study entry. If there is an increase of more than 30% in the levels of ALT, total bilirubin or INR at Day (-14) to Day (-7) [Visit 2] as compared to the values on Day (-42) [Visit 1], then such patients will not be eligible for study entry.

The average of two assessments (Visit 1 and Visit 2) of liver biochemistries and INR will be considered as baseline values for these parameters.

Randomization & Treatment Phase

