4.2 INCLUSION CRITERIA

1. Males or females, between 18 and 75 years of age, inclusive.
2. a) Patients on therapeutic doses of Ursodeoxycholic acid (UDCA) for ≥ 12 months and stable therapy for ≥ 3 months prior to enrolment.
OR
b) Patients who are unable to tolerate UDCA, and did not receive UDCA for at least 3 months from the date of screening.
3. History of confirmed Primary Biliary Cholangitis Diagnosis, based on American Association for the Study of Liver Disease [AASLD] and European Association for Study of the Liver [EASL] Practice Guidelines; [Lindor 2009; EASL 2009], as demonstrated by the presence of at least ≥ 2 of the following 3 diagnostic factors:
 - History of elevated Alkaline Phosphatase levels for at least 6 months prior to Screening Visit 1
 - Positive antimitochondrial antibodies (AMA) titer or if AMA negative or in low titer ($<1:80$) PBC specific antibodies (anti-GP210 and/or anti-SP100 and/or antibodies against the major M2 components [PDC-E2, 2-oxo-glutaric acid dehydrogenase complex])
 - Liver biopsy consistent with PBC.

4. ALP $\geq 1.67 \times$ upper limit of normal (ULN) at Visit 1 and Visit 2 and with $< 30\%$ variance between the levels from Visit 1 to Visit 2.
5. Contraception: Female patients must be postmenopausal, surgically sterile, or if premenopausal, agree to use ≥ 1 effective method of contraception during the trial. Effective methods of contraception are considered to be Hormonal (e.g., contraceptive pill, patch, intramuscular implant or injection); or Double barrier method, i.e., (a) condom (male or female) or (b) diaphragm, with spermicide; or Intrauterine device (IUD); or Vasectomy (partner).
6. Must provide written informed consent and agree to comply with the trial protocol.

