5.2 DOSAGE AND TREATMENT SCHEDULE

Patients will receive either Saroglitazar magnesium 2 mg or Saroglitazar magnesium 4 mg or placebo orally once each morning before breakfast without food (as determined by the patient's schedule) for 16 weeks during the double-blind treatment period. However, during

Approved by: [name]	Protocol No. SARO.16.004 Version No.: 6.0
----------------------------------	--

scheduled visits patients will have the IP administered on site after the blood sample collection.

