5.6 METHOD OF ASSIGNING PATIENT TO TREATMENT GROUP

Patients will be randomly assigned in 1:1:1 ratio to Saroglitazar magnesium 2 mg, Saroglitazar magnesium 4 mg and placebo. The block randomization schedule will be generated using SAS® software (Version: 9.4 or higher; SAS Institute Inc., USA). Each block will contain investigational medicinal products; Saroglitazar magnesium 2 mg, Saroglitazar magnesium 4 mg and placebo. Each block will contain at least 3 kits of IMP for 3 patients i.e., 1 kit of Saroglitazar magnesium 2 mg, 1 kit of Saroglitazar magnesium 4 mg and 1 kits of placebo.

The subject identification number will be established at the site based on the randomization number/kit number/patient number and will be used to identify the subject throughout the study and will be entered on all documentation. The same subject number will not be assigned to more than 1 subject. If a subject is not eligible to receive treatment, or if a subject discontinues from the study, the same subject number cannot be assigned to another subject.

The subjects will first be screened into the study. Once patients are determined to be eligible, they will be randomized. The subject will also be assigned a study drug in accordance to their assigned treatment group upon completion of the randomization.

Patients will be considered randomized as soon as the first allocation of treatment number is assigned. The first study drug intake should take place as soon as possible after randomization (on the same day), under medical supervision.

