7 INVESTIGATIONAL PLAN

7.1 STUDY DESIGN AND PLAN

This is a Phase 2 prospective, multicentre, randomized, double-blind, placebo-controlled study includes a total 36 patients with a diagnosis of Primary Biliary Cholangitis. The study will be conducted over a period of up to 26 weeks and will include a 6-week Screening Phase, a 16-week Treatment Phase and a safety follow-up visit after 4 weeks.

Screening Phase:

- Visit 1 (Day -42): Patient eligibility for participation in the study will be assessed. Medical history will be obtained and physical examination, electrocardiogram (ECG) and laboratory evaluations (including serology, [anti-nuclear antibody, smooth muscle antibody and serum immunoglobulin level G], clinical chemistry, hematology, liver biochemistries, and urinalysis) will be performed. In patients with ANA or SMA antibody positive titers, a liver biopsy must have been performed to rule out autoimmune hepatitis or overlap syndrome. Female patients will undergo a pregnancy test. Serum ALP must be ≥ 1.67 upper limit of normal (ULN) to proceed further in the study.
- Visit 2 (Day -14 to -7): Liver biochemistries (ALT, ALP, total bilirubin (TB) and INR will be re-measured approximately 4 weeks from Day -42 to determine eligibility. Elevated ALP must be ≥ 1.67 ULN on 2 occasions in the Screening Phase and is necessary for study entry. If there is an increase of more than 30% in the levels of ALT, total bilirubin or INR at Day (-14) to Day (-7) [Visit 2] as compared to the values on Day (-42) [Visit 1], then such patients will not be eligible for study entry. The average of two assessments (Visit 1 and Visit 2) of liver biochemistries and INR will be considered as baseline values for these parameters.

Randomization & Treatment Phase:

- Visit 3: The Randomization & Treatment Phase will include 6 outpatient visits over a period of 16 weeks, including the randomization visit. Patients will be randomly assigned to receive either Saroglitzaz magnesium (2 mg or 4 mg) or placebo orally

once daily in addition to their ongoing treatment with UDCA (Patients unable to tolerate UDCA will receive only the investigational medicinal products), starting on Day 1 and continuing for 16 weeks. Efficacy and safety parameters will be assessed during each study visit as per the Schedule Visit Table 1.

- Visit 3.1: Patient will visit study site at 2 weeks after randomization visit for LFTs. The LFTs will be performed at local laboratory.

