After screening, the eligible patients will be randomly assigned to one of the following treatment groups in addition to their ongoing treatment with UDCA (Patients unable to tolerate UDCA will receive only the investigational medicinal products) i.e., Saroglitzaz magnesium 2 mg, Saroglitzaz magnesium 4 mg, or placebo. Vital signs measurements, weight measurements, physical examination, and laboratory examination will be performed as mentioned in Table 1. Concomitant medications will be recorded. AEs will be noted, if any. Urine pregnancy test will be performed for women of childbearing potential. Subjects will undergo cardiac evaluation (ECG). A 4-week supply of study medication (one bottle) will be dispensed. Baseline quality of life assessment will be performed.

- **Visit 3.1 (Week 2±3 Days)**

Patient will visit study site at 2 weeks after randomization visit for LFTs. The LFTs will be performed at local laboratory.

- **Visit 4 (Week 4±3 Days), Visit 5 (Week 8±3 Days) and Visit 6 (Week 12±3 Days)**

Subjects will be undergo a physical examination and laboratory parameters (safety and efficacy) will be assessed as per Table 1. Vitals signs, body weight will be recorded.

AEs, if any, will be noted. Urine pregnancy test will be performed for women of childbearing potential. Concomitant medications will be recorded. Medication compliance will be checked. Medication will be dispensed on each visit for next 4 weeks.

- **End-of-treatment Visit 7 (Week 16±3 Days)**

Subjects undergo physical examination and laboratory parameters (safety and efficacy) will be assessed as per Table 1. Vitals signs and weight will be recorded. AEs will be noted, if any. Subjects will undergo cardiac (ECG) evaluation. Pregnancy test will be performed for all women of childbearing potential. Concomitant medications will be recorded. Medication compliance will be checked.

- **Safety follow-up Visit 8 End of Study (Week 20±3 Days)**

A safety follow-up visit will be performed 4 weeks after End-of-treatment Visit. Patients clinical examination and safety lab assessment will be performed as per Table 1.

Unscheduled visits- will be allowed any time during the study for assessment and management of AEs and any concurrent clinical conditions. Unscheduled visits shall be captured in the CRF.

- If further investigations are required in case of any AE, Investigator will assess the AE and take necessary action, if required.

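### No readable entry criterion explicitly excludes breastfeeding women; pregnancy is largely covered, and an explicit negative-test sentence would only clarify it

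*Protocol*

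**What the plan says.** Inclusion 5, in the synopsis and in section 4.2, is the criterion on reproductive status. A woman must be postmenopausal or surgically sterile or, if premenopausal, must "agree to use ≥ 1 effective method of contraception during the trial". None of the 16 exclusions names pregnancy or breastfeeding.

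Testing is described among the visit procedures. At Visit 1 (synopsis and section 7.1), "Female patients will undergo a pregnancy test"; section 9.4.6 specifies a serum test. For Visit 3, section 7.2 states: "Urine pregnancy test will be performed for women of childbearing potential. Subjects will undergo cardiac evaluation (ECG)". Further tests follow at Visits 4 to 7.

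Two general exclusions could apply indirectly. Exclusion 12 reads "Contraindications to Saroglitzaz magnesium or has any conditions affecting the ability to evaluate the effects of Saroglitzaz magnesium". Exclusion 16 leaves other unsuitable conditions to the investigator's opinion.

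Section 4.4 and section 9.4.6 provide for withdrawal of a subject who becomes pregnant. Section 9.4.6 also contains the only readable mention of lactation: investigators report it if a subject brings it up during the trial or in the four weeks after treatment.

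**The concern.** Agreeing to contraception is a commitment about future conduct. It says nothing about whether a woman is breastfeeding when she enters, and a woman can breastfeed and use contraception at once. No readable procedure asks about breastfeeding, and a pregnancy test does not detect it. Whether such a woman is enrolled then depends on how each of about 10 to 12 sites reads two general exclusions.

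At stake is possible exposure of an infant through a mother dosed daily for 16 weeks. This is a precautionary assumption: the readable text says nothing about transfer of the drug into milk, and the preclinical section is redacted.

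For pregnancy there is a smaller drafting point. The screening text attaches explicit entry consequences to some laboratory results, but attaches none in words to the pregnancy test.

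**Working it through.** There is no figure in the plan to reproduce. The check is a count of the criteria followed by a side-by-side reading.

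**Criteria.** The synopsis and sections 4.2 and 4.3 each give 6 inclusions and 16 exclusions, and both copies are readable in full.

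- Total: 6 + 16 = 22.
- On reproductive status: 1 (inclusion 5).
- Remaining: 22 − 1 = 21, none of which names pregnancy, a test result or breastfeeding.
- Explicitly excluding a breastfeeding woman: 0 of 22.

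**Breastfeeding.**

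| Possible safeguard | Does it reach a breastfeeding woman? |
|---|---|
| Inclusion 5 | No; it concerns contraception |
| Exclusion 12 | Only if breastfeeding is a contraindication; the readable text lists none |
| Exclusion 16 | Only if the investigator judges her unsuitable; the examples given are illnesses |
| Pregnancy tests | No |
| Withdrawal rule | No; it concerns pregnancy |
| Section 9.4.6 on lactation | Reporting only, and only if she mentions it |

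So 2 of the 6 could reach her, and neither names her condition.

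**Pregnancy.** The same question has a different answer.

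- The Visit 1 test is listed under the assessment of eligibility (synopsis and section 7.1), and section 5.6 randomises patients only once they are found eligible.
- The test is repeated at Visit 3. Section 5.6 puts the first dose on the day of randomisation: "The first study drug intake should take place as soon as possible after randomization (on the same day), under medical supervision". Section 5.2 adds that at "scheduled visits patients will have the IP administered on site after the blood sample collection". A test result is therefore due at the visit where staff give the first dose.
- Withdrawal on pregnancy is stated in section 4.4 and repeated in section 9.4.6. Section 9.4.1 dates the course of the trial from signed consent, so the rule can be read to run from then.

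What is missing is one sentence. For a rise in ALT, bilirubin or INR of more than 30%, section 7.1 says "then such patients will not be eligible for study entry". Neither of the 2 pregnancy tests at or before Visit 3 has an equivalent statement.

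**Number affected.** The documents give no rate. Assuming 0 to 1 of the 36 planned patients, the range is 0/36 = 0% to 1/36 = 2.8%.

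**The case against.** The strongest reply concerns what cannot be seen. The visit descriptions defer to Table 1, which is not readable, and sections 2.3 (drug profile) and 5.11 have no readable content. The drug is already marketed in India, so contraindications are presumably defined somewhere, and exclusion 12 would bring them in. If breastfeeding is among them, the eligibility list already excludes these women. This stands as a limit: the finding covers the readable text only. It does not remove the case for naming the exclusion in section 4.3, where sites look for eligibility rules.

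A second reply is that no reasonable investigator would dose a woman with a positive test under a protocol that tests at six visits (1, 3, 4, 5, 6 and 7) and withdraws on pregnancy. This largely succeeds, and it reduces the pregnancy part to a clarification.

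Three stronger readings are tempting but not supported.

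- A reader might infer that the criteria admit breastfeeding women. The text shows only that they do not explicitly exclude them, because the reach of exclusions 12 and 16 is unknown.
- A reader might infer that a pregnant woman could be dosed on a test about six weeks old, since Visit 1 is at Day −42. The repeat test at Visit 3, with first dosing that day, takes most of the weight from that interval.
- A reader might infer from section 7.2 that randomisation precedes the urine test, or that the test precedes dispensing, because "A 4-week supply of study medication (one bottle) will be dispensed" comes after it. The paragraph reads as a checklist, with the baseline quality-of-life assessment after dispensing, so its sentence order settles neither.

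**Conclusion.** The point holds as a minor design matter. Breastfeeding is not explicitly excluded by any of the 22 readable criteria, no readable procedure detects it, and only two general exclusions might apply to it. Pregnancy is largely covered by the tests at Visits 1 and 3 and by the withdrawal rule, and lacks only an explicit sentence.

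The conclusion rests on the readable text; a rule in Table 1, section 2.3 or section 5.11 cannot be ruled out. The protocol describes PBC as mainly a disease of middle-aged women, so few patients are likely to be concerned, but the count remains an assumption. So does infant exposure. No endpoint, analysis or statistical result is affected. Confidence is medium because of the unreadable sections.

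**What to change.** Add to the exclusions in the synopsis and section 4.3: *pregnant or breastfeeding*. Ask about breastfeeding at Visit 1 and record the answer. For clarity, state in section 7.2 that the Visit 3 urine test must be negative before randomisation and the first dose. If Table 1 or another unreadable section already carries such a rule, repeat it in section 4.3 so that all sites work from the same list.

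The cost is one eligibility line, one question and one sentence. The pregnancy tests are already scheduled, so no procedure is added. The downside is that, rarely, one patient is excluded.

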- Visit 3:** The Randomization & Treatment Phase will include 6 outpatient visits over a period of 16 weeks, including the randomization visit. Patients will be randomly assigned to receive either Saroglitzaz magnesium (2 mg or 4 mg) or placebo orally once daily in addition to their ongoing treatment with UDCA (Patients unable to tolerate UDCA will receive only the investigational medicinal products), starting on Day 1 and continuing for 16 weeks. Efficacy and safety parameters will be assessed during each study visit as per the Schedule Visit Table.
- Visit 3.1:** Patient will visit study site at 2 weeks after randomization visit for LFTs. The LFTs will be performed at local laboratory.
- Visits 4, 5 and 6:** Patients will visit the study site at Week 4 (Visit 4), Week 8 (Visit 5) and Week 12 (Visit 6) for clinical assessment, dispensation and reconciliation of study drug, and measurements of efficacy endpoints.
- End-of-treatment Visit (Visit 7):** An End-of-double-blind treatment will occur at Week 16 and considered as End of Treatment visit. The clinical assessment, reconciliation of study drug, and measurements of efficacy and safety endpoints will be performed as per the study schedule.
- Safety Follow-up Visit (Visit 8):** A final post-treatment visit will occur 4 weeks (± 3 days) after the End-of-treatment Visit for safety monitoring. A clinical examination and safety lab assessment will be performed during this visit.

Patient withdrawal

In the event a patient is withdrawn from the study prematurely for any reason, the End of Treatment Visit procedures should be followed.

The Investigator may withdraw a subject from the study for any of the following reasons:

1. Subject who reports AE and if considered in Investigator's/Medical Expert's opinion

that it is not in the subject's best interest to continue.

2. Any subject found to have entered the study in violation of this protocol.
3. Subject's lack of compliance to the study protocol.
4. Any subject who wishes to withdraw his / her consent for participation in the study.
5. In case a subject becomes pregnant, then she will be withdrawn from the trial.
6. Any subject who requires the use of unacceptable concomitant medications as mentioned in exclusion criteria and restrictions.
7. Termination of study by sponsor, IRB/IEC, or the regulatory authority.

Discontinuation of Subject Investigational Product (IP)

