4 STUDY POPULATION

4.1 NUMBER OF SUBJECTS PLANNED

A total 36 subjects (including 20% dropout), will be enrolled on competitive basis at ~10-12 sites in a ratio of 1:1:1 to have 12 subjects in each arm i.e., Saroglitzaz magnesium 2 mg, Saroglitzaz magnesium 4 mg and placebo. Six patients in each group are planned for pharmacokinetic assessment therefore a total of 18 patients will be included. Additional patients may be enrolled into the study to ensure the pharmacokinetic assessment is performed on at least 6 completed patients in each treatment arm. Additional patients will be enrolled if the dropout rate is more than 20%.

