2.3 Randomization

An independent statistician will generate the randomization schedule(s) for study treatment assignment. Eligible subjects will be randomized in a 1:1:1 ratio to receive Saroglitzaz magnesium 2 mg, Saroglitzaz magnesium 4 mg or placebo, respectively. Block randomization will be performed. The randomization schedule will be generated to ensure the treatment balance by using SAS® software (Version: 9.4 or higher; SAS Institute Inc., USA).

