4. SAMPLE SIZE AND POWER CALCULATIONS

This proof of concept study will include a total 36 subjects. No formal sample estimation was done. Subject will be enrolled in 1:1:1 ratio to have 12 subjects in each arm i.e., Saroglitzazar magnesium 2 mg, Saroglitzazar magnesium 4 mg and placebo. Six patients in each group are planned for pharmacokinetic assessment therefore a total of 18 patients will be included. Additional patients may be enrolled into the study to ensure the pharmacokinetic assessment is performed on at least 6 completed patients in each treatment arm. Additional patients will be enrolled if the dropout rate is more than 20%.

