6.4 Statistical Methods for Efficacy Analyses

The primary efficacy endpoint, change from baseline in ALP value at Week 16 will be analyzed separately for Saroglitzazar magnesium 2 mg and 4 mg using a two-sided paired t-test. The primary analysis will be performed using MITT population with LOCF as imputation method for missing values.

The analysis for the secondary efficacy endpoints, change from baseline in ALP at Week 4, Week 8, Week 12 and week 16, change from baseline in lipid profile (TG, TC, HDL, LDL, and VLDL), liver biochemistries (GGT, ALT, AST, bilirubin and albumin), serum total bile acids, 7 α -

Document Title:	Statistical Analysis Plan		
Version Number:	2.0	Date:	11 Nov 2019
Protocol Number:	SARO.16.004	Sponsor Name:	Zydus Discovery DMCC

hydroxy-4-cholesten-3-one (C4) and fibroblast growth factor 19 (FGF 19) and change from baseline in QoL (PBC40) total scores will be analyzed using ANCOVA (Analysis of covariance) model using baseline values and treatment as factors. The p-value for the treatment comparison, estimate of LSMEANS treatment difference (Saroglitazar magnesium (2 mg and 4 mg) – Placebo), and the 95% confidence interval of the LSMEANS difference will be generated from ANCOVA model. Observed and change from baseline values will be summarized descriptively at each visit for all secondary efficacy endpoints.

Frequency and percentage of subjects with ALP improvement of 15%, 20%, 30%, 40% and normalization (achieving abnormal to normal values) at Week 8 and Week 16 will be presented. Difference between the treatment groups will be presented using 95% exact confidence Interval for proportion.

For the PBC40 questionnaire responses, descriptive summaries will be provided for the total and also for each dimensional score.

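### UDCA-treated and UDCA-intolerant patients are randomised together, but neither the block randomisation nor the secondary ANCOVA accounts for UDCA use, so the placebo comparisons and the intolerant-only ALP endpoint are left to chance.

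*Protocol*

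**What the plan says.** Inclusion criterion 2 (Protocol 4.2) has two routes into the trial: at least 12 months on UDCA with the last 3 months stable, or intolerance of UDCA with none taken for at least 3 months. No quota or minimum is set for either. Background therapy therefore differs by design. Under Visit 3 in the Study Protocol Summary, repeated in 7.1 and 7.2, study treatment is added to UDCA in the first group, while for the second "Patients unable to tolerate UDCA will receive only the investigational medicinal products".

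On allocation, Protocol 5.6 states "Patients will be randomly assigned in 1:1:1 ratio to Saroglitazar magnesium 2 mg, Saroglitazar magnesium 4 mg and placebo", with blocks holding at least three kits. Protocol 8.4 repeats the ratio, and SAP 2.3 adds "Block randomization will be performed". None of the three names a stratification factor or says whether blocks are central or held by site.

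On analysis, the primary test is a paired t-test within each active arm (Protocol 8.3.2.1, SAP 6.4). All comparisons with placebo come from an ANCOVA "model using baseline values and treatment as factors" (SAP 6.4; Protocol 8.3.2.2 agrees).

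The Study Protocol Summary, 6.1.2 and 8.3.2.2 list Week 16 ALP change in UDCA-intolerant patients, each dose against placebo, as a secondary endpoint. SAP 6.2 leaves it out, and SAP 6.6 plans no subgroup analysis because the study is small. UDCA use is not among the baseline characteristics named in SAP 5.

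**The concern.** UDCA status is known before randomisation, determines what each patient takes during the trial, and is treated by the protocol as important enough for its own endpoint. With 12 patients per arm and no stratification, the few intolerant patients may fall unevenly. Two things are at stake.

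- If an arm has no intolerant patient, the protocol's intolerant-only comparison involving that arm cannot be made at all.
- If the counts are uneven, each secondary comparison with placebo carries a difference in background therapy for which the model has no term. The same holds for the informal comparison of 2 mg with 4 mg, which matters because the interim analysis is meant to help choose the Phase III dose (Protocol 8.3.5, SAP 2.5).

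**Working it through.** **Inputs.** Sample size: "This proof of concept study will include a total 36 subjects" (SAP 4), so 36/3 = 12 per arm, which agrees with the stated arm size. There is no power calculation to reproduce: "No formal sample estimation was done". The number k of intolerant patients among the 36 is an assumption, because the documents give none; k = 3 to 9 (8% to 25%) is shown.

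**Empty arms.** If allocation ignores UDCA status, the k intolerant patients are a random draw from 36 places.

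- P(a given arm, such as placebo, has none) = C(24,k)/C(36,k).
- P(at least one arm has none) = 3·C(24,k)/C(36,k) − 3·C(12,k)/C(36,k).

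For k = 4: C(24,4)/C(36,4) = 10,626/58,905 = 0.180 and C(12,4)/C(36,4) = 495/58,905 = 0.008. So P(at least one empty) = 3 × 0.1804 − 3 × 0.0084 = 0.516.

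| k | Placebo has none | At least one arm has none |
|---|---|---|
| 3 | 28% | 76% |
| 4 | 18% | 52% |
| 5 | 11% | 33% |
| 6 | 7% | 21% |
| 9 | 1% | 4% |

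Blocking that ignores UDCA does not help. Simulating one central list with blocks of three gives 76%, 51%, 33%, 21% and 4% in the last column.

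**Uneven counts.** Enumerating the counts (x, y, z) over three arms of 12, with probability C(12,x)·C(12,y)·C(12,z)/C(36,k), gives the chance of a difference of three or more intolerant patients:

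| k | One given dose vs placebo | Either dose vs placebo |
|---|---|---|
| 4 | 11% | 20% |
| 6 | 18% | 28% |
| 9 | 25% | 38% |

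**Effect on a contrast.** A difference of 3 in 12 shifts an unadjusted arm difference by (3/12)·d, where d is the difference in mean ALP change between the two UDCA groups in SD units. The documents give no d. For assumed d = 0.25 to 1.0 the shift is 0.06 to 0.25 SD. The standard error of a difference between two arms of 12 is √(2/12) = 0.41 SD.

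**What stratification would do.** On one central list, with blocks of three within each UDCA group from the first patient, every arm has at least one intolerant patient once k reaches 3, and counts differ by at most one. The arms then hold 1, 1, 1 at k = 3; 1, 1, 2 at k = 4; 1, 2, 2 at k = 5; and 2, 2, 2 at k = 6.

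**The case against.** Several points on the other side are sound.

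**The primary test is untouched.** A reader might infer that imbalance undermines the primary result. It does not: each active arm is compared with its own baseline, so the mix in another arm cannot change that p-value.

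**Chance imbalance is not bias.** Over repeated randomisations the contrasts are unbiased, and the confidence intervals already allow for such imbalance. The computed shift is smaller than one standard error throughout the assumed range. This stands. What remains is avoidable loss of precision and a harder reading of one small trial.

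**Part of the difference is already absorbed.** UDCA is stable at entry and continues unchanged, endpoints are changes from baseline, and the ANCOVA adjusts for baseline. Level differences are therefore largely dealt with; a different response by background therapy is not. The SAP's concomitant-medication summary by arm should also reveal UDCA use, though only indirectly.

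**Balance does not rescue the intolerant-only comparison.** Where an empty arm is likely, perfect balance still gives only one or two such patients per arm. This stands, and it is why the endpoint should be descriptive.

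**The guarantee needs a central list.** Protocol 5.6 describes blocks as sets of kits, and about 10–12 sites take part. If blocks are held and stratified by site (11 sites assumed, blocks of three), simulation leaves the chance of an empty arm at about 75%, 48%, 30% and 17% for k = 3, 4, 5 and 6, little better than no stratification.

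**A UDCA main effect does not separate monotherapy from add-on effects.** That would require an interaction, which 36 patients cannot support.

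**Conclusion.** The gap is real and limited in scope. The plan knowingly mixes two background-therapy groups and names an endpoint in one of them, but accounts for UDCA use in neither the allocation nor the secondary model. The comparisons with placebo, the comparison of doses and the intolerant-only endpoint are affected; the primary within-arm tests are not.

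The size depends on k, which is unknown. Up to about k = 6 an empty arm is the main risk (21% at k = 6, rising to 76% at k = 3). By k = 9 that risk is 4%, and uneven counts dominate (25% for a given dose against placebo, 38% for either). How far a contrast then moves rests wholly on an assumed difference in response. The documents do not support reading this as systematic bias or as a threat to the primary conclusion. Changes this cheap should still be made.

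**What to change.** 1. **Model and baseline table.** Add UDCA use at entry (on UDCA / intolerant), already established by inclusion criterion 2, as a two-level factor in the SAP 6.4 ANCOVA models, and report it by arm in the SAP 5 baseline table. Fix this before the interim unmasking; SAP 1 allows revisions before database lock. The cost is one residual degree of freedom: 36 − 3 arms − 1 baseline slope = 32, falling to 31. The term adjusts for a main effect only and will be imprecise if k is very small.

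2. **Randomisation.** For patients not yet randomised, stratify the blocks in Protocol 5.6, Protocol 8.4 and SAP 2.3 by UDCA use, on one central list, and state that it is central. The cost is a second list and kit sequence and possibly one more incomplete block. Started part-way through enrolment, it improves balance among the remaining patients but no longer ensures an intolerant patient in every arm.

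3. **Intolerant-only endpoint.** Reconcile its listing in the Study Protocol Summary, 6.1.2 and 8.3.2.2 with its absence from SAP 6.2 and the statement in SAP 6.6. Report it descriptively, with counts and individual changes by arm. The cost is a short amendment and one table.
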